As part of a sensitivity analysis we will fit adapt the primary model to include the pupillevel pre-test score, but centred around school means, and include an additional school-level average pre-test score at level 2. This follows the advice of Hedges and Hedberg (2013, p450) and Bafumi and Gelman (2006) to reduce the correlation between the pre-test and the schoollevel units which can cause poor estimates of uncertainty in the parameters.

Longitudinal follow-up analyses³

There has been some discussion of conducting a further study on the longitudinal outcomes of Glasses in Classes at the stage of the KS1 examinations. The results of these tests could be collected from schools or requested from the NPD. At this stage it remains an option and

7

³ Please see the longitudinal analysis guidance.

if approved, an addendum would be added to the analysis plan and the final report. The model will remain the same format as the primary analysis.

Imbalance at baseline

While we will focus on the imbalance for the primary measure (the Woodcock Johnson IV Letter-Word ID) in terms of pupil (baseline pre-test and FSM status) and school characteristics (Ofsted rating, rural-urban classification, percentage of FSM pupils), we will provide supplementary imbalance characteristics for the three further secondary measures – the Woodcock Johnson IV Applied Problems and Word Attack subscales, and the visual acuity logMAR measure. This will be presented as a cross-tabulation with means, standard deviations and effect sizes for continuous variables and counts and percentages for categorical variables.

Missing data

As per EEF standards, headline figures will be presented throughout. In addition, as set out in Corcoran (2016, p.69) we will carry out an analysis to examine the overall and differential attrition rates that may bias the estimated impact of the Glasses in Classes treatment condition. However, there is an expectation that overall attrition would be less than 10% and the difference between the treatment and control schools less than 5%. These thresholds being within acceptable standards for WWC guidelines (WWC Standards and Procedures Handbook, Version 4.1). This expectation for low attrition and potential for bias is due to random factors and the primary reason for pupil attrition being independent of the treatment, such as families moving. However, attrition at the pupil level will be monitored and the structure of the missing data will be assessed using the MCAR test (Little, 1988). If the structure of the missing data is not missing completely at random (MCAR) or the combination of a non-MCAR test results and pupil overall attrition that is above a 5% threshold, then multiple imputation methods will be considered for a sensitivity analysis (Little and Rubin, 2002).

Compliance

The comparison group variable will be used as the instrumental variable to predict compliance which is a dichotomously measured indicator that distinguishes between the randomly assigned treatment and comparison students. The use of the comparison group is standard per WWC guidelines (WWC Standards Handbook, Version 4.1, p. 46). The variable that will be used as the endogenous independent variable that estimates compliance will be a dichotomous variable that indicates full fidelity vs incomplete fidelity of implementation. The fidelity variable could be derived from two fidelity sub-domains: child attendance with optometrist with prescription glasses and whether the pupil had a full set (two pairs of glasses) compared to a single set or no glasses. These variables could be combined into an index and then dichotomised based on full fidelity. Full fidelity and optimal compliance would consist of those pupils that had greater than 80% attendance (percent of total optometrist sessions attended) with the optometrist and had a full set of prescription glasses. The use of the compliance variable as a dichotomous endogenous independent variable is consistent with WWC guidelines (WWC Standards Handbook, Version 4.1, p. 46). The level at which compliance is measured is at the pupil level.

To assess treatment effects in the presence of non-compliance, CACE analysis will be conducted using a Two-stage least squares (2SLS) analysis that utilizes asymptotic standard errors. The first-stage of the analysis will be specified as:

Compliance
$$y_i = \beta_{0i} + \beta_1 Treatment_i + \beta_2 Pretest Outcome_i + \varepsilon_i$$

Where, i is notation for all individuals in the sample, Compliance y is the endogenous independent variable that measures compliance with the treatment measured as a dichotomous variable, Treatment is a dichotomous variable that captures the random assignment of students to treatment or control groups by school, the Pretest outcome is the pretest measure of the outcome variable, and ε is the error term. This first stage equation is

estimated using OLS and predicted values of the compliance variable will be generated from these estimates and denoted as Compliance \hat{y}_i for the final stage of analysis. The predicted compliance indicator will measure the contrast between those intervention pupils with optimal compliance to the intervention and those intervention pupils with minimum compliance to the intervention in addition to control pupils.

The structural equation with the final stage will be specified as:

Posttest Outcome
$$y_i = \beta_{0i} + \beta_1 Compliance \hat{y}_i + \beta_2 Pretest Outcome_i + \varepsilon_i$$

Where, Outcome y is the posttest outcome of interest, Compliance \hat{y} is the predicted values of the endogenous independent variable that measures compliance from the first stage of analysis, Treatment is a dichotomous variable that captures the random assignment of students to treatment or control groups by school, Pretest outcome is the pretest measure of the outcome variable, and ε is the error term.

In terms of measuring compliance properly, if the theoretical thresholds for both the attendance with optometrists and pairs of glasses received do not exceed adequate thresholds of the intervention group sample, this may suggest that the theoretical thresholds for attendance may be too strict. In that instance, a Jenks natural breaks optimisation will be conducted on the attendance fidelity measure using raw percentage of attendance (Jenks 1967). This will be done to determine an adequate classification of attendance and inclusion for the purposes of compliance with the study intervention.

In sum, this CACE analysis will be used to assess the potential impact of random assignment and other covariates on compliance with the treatment. These estimates in turn will be used along with all covariates to predict the outcome of interest and therefore provide an unbiased estimate of the impact of compliance and non-compliance on the outcome. Hedge's g will be calculated to determine the effect size. Statistically insignificant and non-meaningful effects of the compliance variable will indicate that noncompliance in the study did not have an impact on the outcomes.

Intra-cluster correlations (ICCs)

Intra-cluster correlations (ICCs) will be calculated from a multilevel null model (i.e. one without the treatment or pre-test covariates, but including the school level) for the primary reading achievement outcome. The formula is presented below. As part of the appendices we will also provide ICC calculations for the secondary reading, mathematics and visual acuity outcomes.

$$ICC = \frac{\sigma_{school}^2}{(\sigma_{school}^2 + \sigma_y^2)}$$

Effect size calculation

EEF standard practice will be followed in reporting effect sizes (Hedges *g*). The formula is presented below:

$$ES = \frac{\overline{Y}^t - \overline{Y}^c}{\sqrt{(\sigma_{school}^2}^2 + \sigma_y^2)}$$

Effect size quantities will be computed from the Ime4 using the sim() function in the Applied Regression Modelling package (arm) in R to generate a posterior distribution from which 95% confidence intervals can be calculated.

References

- Bafumi, J. & Gelman, A. (2006) Fitting multilevel models when predictors and group effects correlate. 2006 Annual Meeting of the Midwest Political Science Association, Chicago, II.

 http://www.stat.columbia.edu/~gelman/research/unpublished/Bafumi_Gelman_Midwest06.pdf

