#### Randomisation

The proposed design involves a randomised multi-level/hierarchical trial, with school level randomisation using a simple randomisation process. School assignment will be completed for all schools in autumn 2019 for a total of 100 schools (50 control, 50 treatment).

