Pre-test/ post-	level 1 (pupil)	0.88 ¹	0.88	0.88	0.88
test	level 2 (class)	-	-	-	-
correlations	level 3 (school)	0.62	0.62	0.62	0.62
Intracluster	level 2 (class)	-	-	-	-
correlations (ICCs)	level 3 (school)	0.15 ²	0.15	0.15	0.15
Alpha		0.05	0.05	0.05	0.05
Power		0.8	0.8	0.8	0.8
One-sided or two-sided?		Two-sided	Two-sided	Two-sided	Two-sided
Average cluster size		7	3	8	
	intervention	50	50	50	50
Number of schools	control	50	50	49	49
	total	100	100	99	99
	intervention	350	150	406	

¹ Villarreal (2015) undertook a test review of the WJIV standard battery of tests and found correlations in the range of .83-.95. In the Woodcock Johnson IV manual, test-retest correlations were between 0.83-0.95 for the age 7-11 group (p.94). However, these sort of test-re-test reliability analyses tend to be over very short periods (e.g. one day).

² We have selected an ICC of 0.15 as this represents a trade-off in that the schools are centred on a specific small geographical region, but on the other hand recognises that some EEF trials amongst Early Years have been higher at 0.17-0.19.

		Prot	Protocol		nisation
		OVERALL	FSM	OVERALL	FSM
Number of pupils	control	350	150	387	
	total	700	300	793	

With the above parameters, at the protocol stage, we estimated that it is possible to achieve an MDES of 0.195 for the main effect and 0.22 for FSM subgroup analysis. During recruitment we found that the number of children failing their initial vision screening was slightly higher than expected giving an average cluster size of 8 children in the study. Despite recruiting one school less than planned, the MDES remained effectively stationary at 0.194. The FSM estimate at randomisation will be updated once we receive the matched data from the DfE containing the FSM indicator.

Analysis

The analysis will examine the impact of the Glasses in Classes intervention in comparison to the business-as-usual control condition on the basis of intention to treat (ITT) using a two-level multilevel model using Maximum Likelihood estimation.

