Error terms in linear regression are assumed to be independent. However, pupils are clustered within schools and are considered more similar than those pupils attending other schools, violating this key assumption. Multilevel modelling allows us to relax the independence assumption and represents a compromise approach between complete pooling approaches where all schools are treated the same within the model, and no pooling approaches where a separate model is fitted for each school. Multilevel modelling allows partial pooling where the effect of schools with little data are pooled towards the mean (Gelman & Hill, 2007, p252-259). Practically speaking multilevel models tend to provide the similar point estimates to complete pooling models, but have larger more appropriate standard errors and confidence intervals.

Primary outcome analysis

As discussed in table 1 above we will investigate the main outcome – the impact on reading achievement as measured by Woodcock Johnson IV Letter-Word Identification subscale. We will use the standardised score for both post and pre-test. As randomisation took place at the school-level, the post-test score will be modelled using a varying intercept model which is presented below follows:

$$\begin{aligned} \mathcal{Y}_{ij} &= \beta_{0j} + \beta_{1} Treatment_{ij} + \beta_{2} Pre - Test_{ij} + u_{0j} + \varepsilon_{ij} \\ & u_{0j} \sim N \; (0, \sigma_{school}^{2}) \\ & \varepsilon_{ij} \sim N \; (0, \sigma_{y}^{2}) \end{aligned}$$

This can be understood as follows. The post-test score for the i^{th} student in the j^{th} school is equal to the grand mean score (β_{0j}) , the impact of a binary indicator denoting treatment received (β_1) which is coded as 0 or 1, the impact of the mean-centred normally distributed pre-test (β_2) , the school-level error term (u_{0j}) , and finally the student-level error term (ε_{ij}) . The two error terms each receive their own probability distribution which are assumed to be normally distributed and centred on 0, with the two variance parameters estimated from the data $(\sigma^2_{school}$ and $\sigma^2_{v})$.

Secondary outcome analysis

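### The stated MDES assumes separate pupil- and school-level pre-test adjustment, but the primary model has a single pre-test slope; baseline logMAR is also left out of the reading and mathematics models

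*SAP*

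**What the plan says.** In the SAP, Primary outcome analysis, the Letter-Word post-test is regressed on treatment, one pre-test term ("the impact of the mean-centred normally distributed pre-test") and a school random intercept. The protocol's Analysis plan gives the same model.

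The sample-size tables (protocol Table 3, SAP Table 2) enter two pre/post correlations, 0.88 at pupil level and 0.62 at school level. They report an MDES of 0.195 at protocol stage and 0.194 at randomisation.

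Under Additional analyses, the SAP adds a sensitivity model that centres the pupil pre-test on its school mean and would "include an additional school-level average pre-test score at level 2". The stated reason is a correlation between the pre-test and the school units "which can cause poor estimates of uncertainty in the parameters".

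Baseline logMAR is collected in autumn 2019, before randomisation. It selects the analysis sample (0.2 or greater; protocol, Design), is the baseline for the visual acuity outcome, and appears in the imbalance table. It is not in the reading or mathematics models. Allocation is by "school level randomisation using a simple randomisation process", without stratification.

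**The concern.** An MDES should describe the model that will be reported as primary. This one credits a school-level pre-test adjustment that the primary model makes only indirectly, through a slope set almost wholly by differences between pupils within schools. If the within-school and between-school slopes differ, the single slope over- or under-adjusts the school means. Treatment is assigned to schools, so the school level dominates the standard error. The SAP names a weakness of this kind and gives the remedy only sensitivity status.

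Separately, poor vision is the deficit the programme targets, and the protocol's rationale treats it as a cause of weaker early reading and mathematics. With unstratified allocation of 99 schools, a chance difference in baseline acuity would be tabulated but not adjusted for in the academic models.

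**Working it through.** **Inputs from SAP Table 2.** Alpha 0.05 two-sided; power 0.8; school ICC 0.15 ("We have selected an ICC of 0.15 as this represents a trade-off"); correlations 0.88 (pupil) and 0.62 (school). Protocol stage: 100 schools of 7. Randomisation: 99 schools (50:49) and 793 pupils, so n = 793/99 = 8.01.

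**Not given, so assumed.** Pre-test ICC (ρx), varied from 0.05 to 0.25.

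**Step 1: reproduce the stated figure.**

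MDES = M × √{[ICC(1 − R²school) + (1 − ICC)(1 − R²pupil)/n] / [P(1 − P)J]}, where M = t(0.975) + t(0.80) on J − 3 df ≈ 2.83, R²pupil = 0.88² = 0.774 and R²school = 0.62² = 0.384.

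- Protocol: 0.15 × 0.6156 = 0.0923; 0.85 × 0.2256/7 = 0.0274; 2.83 × √(0.1197/25) = 0.196 (stated 0.195).
- Randomisation: 0.0923 + 0.1918/8.01 = 0.1163; P(1 − P)J = 50 × 49/99 = 24.75; 2.83 × √(0.1163/24.75) = 0.194 (stated 0.194).
- At protocol stage, other readings miss: correlations used directly as R² give 0.151, squaring only one gives 0.164 or 0.185, and R²school = 0 gives 0.238.

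So the stated MDES rests on separate R² values at the two levels. Between-school variance is 0.0923/0.1163 = 79% of the error variance at n = 8.

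**Step 2: the single-slope primary model (99 schools).** The within-school slope is bw = 0.88√(0.85/(1 − ρx)) and the between-school slope is bb = 0.62√(0.15/ρx). The model fits one slope β, a precision-weighted mix of the two, solved iteratively with the variances (large-sample). Residual variances:

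- school: T = 0.15 − 2β·bb·ρx + β²ρx
- pupil: s² = 0.85 − 2β·bw(1 − ρx) + β²(1 − ρx)

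At ρx = 0.15: bw = 0.88, bb = 0.62, β = 0.871. T = 0.15(1 + 0.871² − 2 × 0.871 × 0.62) = 0.1018 and s² = 0.1918. MDES = 2.83 × √[(0.1018 + 0.1918/8.01)/24.75] = 0.202.

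**Step 3: add the observed school mean.** The error variance of a school mean is V_Y − C²/V_X, with V_Y = 0.15 + 0.85/n, V_X = ρx + (1 − ρx)/n and C = bb·ρx + bw(1 − ρx)/n. At ρx = 0.15: V_Y = V_X = 0.2561 and C = 0.1864, leaving 0.1205 before rounding. MDES = 2.83 × √(0.1205/24.75) = 0.198.

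| Assumed pre-test ICC | Single slope | School mean added |
|---|---|---|
| 0.05 | 0.196 | 0.196 |
| 0.10 | 0.195 | 0.194 |
| 0.15 | 0.202 | 0.198 |
| 0.20 | 0.214 | 0.202 |
| 0.25 | 0.230 | 0.206 |

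At the protocol-stage size (100 schools of 7) and ρx = 0.15, the pair is 0.203 and 0.200.

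**Step 4: a lower pupil correlation.** The SAP's own footnote warns that 0.88 reflects retests over very short intervals. With an assumed 0.7, the two models give 0.218 and 0.218 at ρx = 0.15, and 0.228 and 0.221 at 0.25. With 0.6 they give 0.228 and 0.228, then 0.231 and 0.229. The largest gain over the whole ICC range is about 0.007.

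**Step 5: baseline logMAR.** No document gives its correlation with reading. If it removed an assumed 0, 2, 5 or 10% of residual variance at both levels, the Step 1 MDES of 0.194 would become 0.194, 0.192, 0.189 or 0.184.

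**The case against.** The strongest reply is that little turns on this. The school-mean model is already pre-specified with its rationale, so both results will be reported. At a pre-test ICC of 0.05 to 0.10 the models are practically equal, and a large gap needs an ICC of 0.20 or more. A pupil correlation of 0.6 to 0.7 over two years would raise the MDES to roughly 0.22 to 0.24 under either model, which matters more than the choice between them at most ICC values. All of this stands and limits the size of the point. It does not remove the mismatch between the stated MDES and the primary model.

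Four stronger readings are tempting, and the documents do not support them:

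- **The primary model gets no school-level adjustment, so its MDES is 0.237 at 99 schools.** The sensitivity model is distinguished by centring on school means, which implies grand-mean centring in the primary model. A pre-test centred that way also absorbs between-school variance, so 0.237 is only an upper bound.
- **Adding the school mean restores the stated MDES exactly.** The observed mean of about 8 pupils carries sampling error. At a pre-test ICC of 0.15 the result is 0.198, not 0.194.
- **Baseline logMAR is unused, and adding it is free precision.** It has three uses already. Its range is cut at 0.2, the reading pre-test may already carry much of its information, and the gain could be nil.
- **The unadjusted estimate is biased.** Under randomisation it is not, and its standard error allows for chance imbalance. One pre-specified covariate is legitimate.

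**Conclusion.** The mismatch is real and minor. The stated 0.195/0.194 reproduces only with level-specific adjustment, which is the structure of the SAP's sensitivity model. At the plan's correlations the single-slope primary model has an MDES between about 0.195 and 0.230, depending on a pre-test ICC that the documents do not give; at an assumed 0.15 it is about 0.20. In every case tried, the school-mean model did as well or better after paying for its degree of freedom, with gains from almost nothing to 0.024 (0.230 − 0.206). These figures are large-sample approximations with equal cluster sizes and no attrition.

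For logMAR the argument is protection against chance imbalance in the targeted deficit. A power gain cannot be claimed from the documents.

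**What to change.** Before outcome data are seen:

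1. Make the school-centred pupil pre-test plus school-mean pre-test the primary model, and keep the single-slope model as the sensitivity analysis. If the single-slope model stays primary, restate its MDES as about 0.20 at the plan's inputs, and show the assumed pre-test ICC and its range.
2. Add baseline logMAR as a covariate in the reading and mathematics models. State which score is used, since the Outcome measures section does not say which eye or combination enters the analysis, and give a rule for missing baseline values.

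The cost is SAP wording and about two degrees of freedom out of some 97 (99 schools less 2). No new data are needed. The SAP still describes a reception-year outcome and needs revising for the two-year trial, so both changes can go into that revision.

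### The CACE analysis is specified as single-level 2SLS with no allowance for school clustering, so at the SAP's planning values its nominal 5% test would reject about 16–28% of the time

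*SAP*

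**What the plan says.** In the SAP's Compliance section, "CACE analysis will be conducted using a Two-stage least squares (2SLS) analysis that utilizes asymptotic standard errors". The first stage regresses a dichotomous pupil-level compliance variable on allocation and pre-test. The second regresses the post-test on predicted compliance and pre-test. Both equations carry a single subscript, explained as "i is notation for all individuals in the sample", and a single error term. The first stage is "estimated using OLS and predicted values of the compliance variable will be generated from these estimates". School enters only through the definition of the treatment indicator, which is assigned by school. Neither stage has a school random effect, and no cluster-robust or bootstrap variance is mentioned.

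The Analysis section of the same SAP reasons differently for the ITT model. It states: "Error terms in linear regression are assumed to be independent. However, pupils are clustered within schools". It goes on to say that this breaks the independence assumption and that multilevel models "have larger more appropriate standard errors and confidence intervals". The Primary outcome analysis section then includes a school term on the ground that "As randomisation took place at the school-level". That two-level model is tied to the ITT analysis, and nothing extends it to the CACE.

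The Compliance section also draws an inference from the CACE test: "Statistically insignificant and non-meaningful effects of the compliance variable will indicate that noncompliance in the study did not have an impact on the outcomes".

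**The concern.** The instrument is constant within a school. Information about its effect therefore comes from differences between about 50 and 49 school means, not from 793 independent pupils. A conventional 2SLS variance treats all pupils as independent and gives an interval that is too narrow.

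With one binary instrument and the same covariate in both stages, the 2SLS estimate equals the pupil-level effect of allocation on the outcome divided by the effect of allocation on compliance. Its test should therefore agree closely with the ITT test. If the ITT model allows for clustering and the CACE does not, the CACE can appear significant when the ITT estimate from the same data is not. A reader could take this as evidence that the programme works for children who comply, when the difference comes only from the variance formula. The SAP plans to interpret the significance of this coefficient, so the error rate has a direct consequence.

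**Working it through.** **Inputs (SAP, Table 2, randomisation columns).** School ICC 0.15; pre/post correlation 0.88 (pupil) and 0.62 (school); 99 schools (50 and 49), 793 pupils, 793/99 = 8.01 per school; two-sided alpha 0.05.

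**Reproducing the SAP's own figure.** MDES = [t(0.975) + t(0.80)] × √{ρ(1 − R²_school)/(P(1−P)J) + (1−ρ)(1 − R²_pupil)/(P(1−P)Jn)}, with R²_pupil = 0.88² = 0.774 and R²_school = 0.62² = 0.384.
- At randomisation (J = 99, n = 8, 97 df): 2.83 × √(0.00373 + 0.00097) = 0.194. The SAP states 0.194.
- At protocol stage (J = 100, n = 7): 0.196. The SAP states 0.195.

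The two values are therefore used as correlations and squared, and the same reading is used below.

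**Residual ICC after the pre-test.**
- School variance: 0.15 × (1 − 0.384) = 0.0923.
- Pupil variance: 0.85 × (1 − 0.774) = 0.1918.
- Residual ICC: 0.0923/(0.0923 + 0.1918) = 0.325.

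This exceeds 0.15 because the pre-test removes more pupil variance than school variance.

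**Design effect and true size.** DE = 1 + (m − 1) × ICC, and the actual size of a nominal 5% test that ignores schools is 2Φ(−1.96/√DE).

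| ICC used | m | DE | √DE | Actual size |
|---|---|---|---|---|
| 0.15 (no pre-test adjustment) | 7 | 1.90 | 1.38 | 15.5% |
| 0.15 (no pre-test adjustment) | 8 | 2.05 | 1.43 | 17.1% |
| 0.325 (given pre-test) | 7 | 2.95 | 1.72 | 25.4% |
| 0.325 (given pre-test) | 8 | 3.28 | 1.81 | 27.9% |

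**Simulation of the SAP's two equations.** 99 schools of 8, no treatment effect, no compliance in controls, 50% compliance in the intervention arm (assumed), 3,000 runs:
- Pupil correlation 0.88: conventional 2SLS rejects 27.7%. The mean reported standard error is 0.077 and the empirical standard deviation of the estimate is 0.143, a ratio of about 1.85. School-clustered standard errors reject 5.3%.
- Pupil correlation 0.7, 0.6 and 0.5 (assumptions): conventional 2SLS rejects 18.4%, 16.3% and 14.9%. At 0.6 the standard error ratio is 1.42.

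A separate simulation (793 pupils, 4,000 runs per scenario) gave 30.0% at the planning values, with 29.6% to 30.0% when compliance was set at 30%, 60% or 90%. It gave 16.5% with the ICC lowered to 0.05 (assumed) and 35% with unequal school sizes (coefficient of variation 0.5, assumed). School-clustered errors rejected between 4.8% and 5.7% in all scenarios.

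**Why the simulated ratio slightly exceeds 1.81.** The SAP's equations have one pre-test coefficient, not separate pupil and school slopes.
- Coefficient: 0.85 × 0.88 + 0.15 × 0.62 = 0.841.
- School residual variance: 0.15 × (1 + 0.841² − 2 × 0.841 × 0.62) = 0.0997.
- Pupil residual variance: 0.85 × (1 + 0.841² − 2 × 0.841 × 0.88) = 0.1931.
- Residual ICC 0.0997/(0.0997 + 0.1931) = 0.341; DE = 1 + 7 × 0.341 = 3.38; √DE = 1.84; size 28.7%.

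The simulated 27.7% and 30.0% both lie within two simulation standard errors of this value.

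**The case against.** - **Wording.** The SAP says only that the standard errors are asymptotic. Cluster-robust errors are asymptotic too, and the SAP's subscripts are loose elsewhere. It is therefore an inference that unclustered errors are meant. This stands as a caution, but single-level equations with no mention of clustering give an analyst no reason to do otherwise. If clustering was intended, the SAP still has to say so.
- **Magnitude.** The range 16–28% is not a figure in the documents and is not a bound. The upper end depends on the 0.88 pupil correlation, which the SAP's own footnote links to retests over very short periods, while this trial tests about two school years apart. This is fair: a weaker correlation lowers the residual ICC and moves the result towards the lower end. A lower ICC reduces it further. By formula, with pupil correlation 0.5–0.6 and 8 per school, size is 8–9% at an assumed ICC of 0.05 and 12–13% at 0.10. In the other direction, an ICC of 0.19 with correlation 0.88 gives 31%, and unequal school sizes raise it further. Every case examined exceeds 5%.
- **Importance.** The CACE is supplementary. The primary, secondary and subgroup models include a school effect, and the CACE point estimate is not in dispute. This limits the consequence to the CACE interval and test, but does not make them valid.
- **Two-stage computation.** The SAP names OLS only for the first stage, so a literal second OLS on fitted values is not certain. Fitting both stages in one routine is therefore a clarification, not the correction of a proven error.

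**Conclusion.** The concern holds. Followed as written, the CACE analysis gives an interval that is too narrow and a test that rejects too often, for the reason the SAP itself gives when justifying a multilevel ITT model. At the SAP's ICC of 0.15 and 8 pupils per school, the true standard error is about 1.4 times the reported one if the pupil correlation is 0.6 (assumed), and about 1.8 times if it is 0.88 (the planning value). The corresponding type I error is about 16% and 28%. These figures assume near-equal school sizes and compliance that is independent between pupils in the same school. The conclusion that size exceeds 5% does not depend on the exact inputs. The ITT results and the MDES are not affected.

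**What to change.** In the Compliance section, replace the reference to asymptotic standard errors with school-level cluster-robust standard errors for the 2SLS estimate, using a t reference with number of schools minus 1 degrees of freedom. With 99 schools the choice of degrees of freedom matters little. A bootstrap that resamples whole schools and refits both stages is an acceptable alternative. State that both stages are fitted in one instrumental-variable routine, because standard errors from a second OLS on fitted values are wrong even without clustering. The point estimator stays as planned.

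The cost is one sentence in the SAP and one option in the IV command, with no new data. The CACE interval becomes wider, by a factor of roughly 1.4 to 1.85 over the correlations of 0.6 to 0.88 considered above.

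### The SAP misdescribes what its predicted compliance variable measures, omits the assumption the CACE needs, and fixes in advance readings of the coefficient that do not follow.

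*SAP*

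**What the plan says.** All of this is in the SAP's Compliance section.

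- Instrument: "The comparison group variable will be used as the instrumental variable to predict compliance".
- Endogenous variable: "a dichotomous variable that indicates full fidelity vs incomplete fidelity of implementation". Full fidelity means "those pupils that had greater than 80% attendance (percent of total optometrist sessions attended) with the optometrist and had a full set of prescription glasses". Its glasses component is "whether the pupil had a full set (two pairs of glasses) compared to a single set or no glasses", so a pupil with one pair is coded 0.
- First stage: ordinary least squares of compliance on Treatment and the pre-test, where "Treatment is a dichotomous variable that captures the random assignment of students to treatment or control groups by school". Then "predicted values of the compliance variable will be generated from these estimates", and these replace observed compliance in the outcome equation, which also contains the pre-test.
- Description of the predictor: "The predicted compliance indicator will measure the contrast between those intervention pupils with optimal compliance to the intervention". The sentence goes on to name the other side of the contrast as the intervention pupils who complied least together with the control pupils.
- Planned reading: the analysis will "provide an unbiased estimate of the impact of compliance and non-compliance on the outcome". The section ends by saying that a compliance coefficient that is neither significant nor meaningful will be taken to show that non-compliance did not affect the outcomes.

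The section does not state the exclusion restriction or monotonicity, and it does not define the complier population.

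**The concern.** The description of the predictor fits the variable before it is predicted, not after. Taken with the closing paragraph, it invites the reader to treat the coefficient as a measure of how much compliance mattered. The coefficient is a rescaled arm difference. It bears on compliance only through an assumption that the SAP leaves out and that the intervention's design strains. The Protocol's process evaluation asks about fidelity and about delivery at scale, so a compliance effect read wrongly would bear on questions the evaluation itself poses.

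**Working it through.** The plan gives no figure to reproduce for this point: no compliance rate and no expected CACE. The check is algebra on the SAP's two equations, with a simulation to confirm it.

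**1. What the predictor can distinguish.** Predicted compliance = a + b × Treatment + c × pre-test. Two intervention pupils with the same pre-test get the same value, whatever they did. The pre-test is also in the second stage, so the only variation left to identify the coefficient is allocation.

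**2. What the coefficient is.** With one binary instrument and the same covariate in both stages,

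coefficient = (adjusted arm difference in outcome) / (adjusted arm difference in full-fidelity rate).

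Both parts come from single-level regressions on Treatment and pre-test. The primary model adds a school intercept, so its ITT estimate may differ slightly from this numerator. The coefficient is zero exactly when the numerator is zero.

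**3. Simulation of both equations.** From SAP Table 2: 99 schools (50 and 49), 8 pupils each, ICC 0.15. Assumed: 60% full fidelity in the intervention arm and none in control; an effect of 0.20 SD in full compliers and none in other pupils; an unmeasured trait raising both compliance and outcome; 600 replicates.

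- The coefficient equals the ratio in step 2 to rounding error (below 1e-14).
- The gap in predicted compliance between full and other intervention pupils averages about 0.001. Between arms it is about 0.60.
- The mean coefficient is 0.197 against a true 0.20. A direct comparison of full with other pupils inside the intervention arm gives 0.65, because those groups are self-selected.

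So the 2SLS number is sound when its assumptions hold, and it is not a within-arm contrast.

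**4. What happens if partial delivery helps.** This illustrates a breach of the exclusion restriction under assumed rates and effects. It does not measure the size of the wording error. Let p be the full-fidelity rate in the intervention arm (zero in control), d the effect in full compliers, and k the effect in the remaining intervention pupils. Then

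coefficient = [p × d + (1 − p) × k] / p = d + k × (1 − p)/p.

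With d = 0.20:

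| k | p = 40% | p = 60% | p = 80% | True full minus partial |
|---|---|---|---|---|
| 0 | 0.20 | 0.20 | 0.20 | 0.20 |
| 0.10 | 0.35 | 0.27 | 0.225 | 0.10 |
| 0.20 | 0.50 | 0.33 | 0.25 | 0 |

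For example, at k = 0.10 and p = 40%: 0.20 + 0.10 × 0.60/0.40 = 0.35. If k is above zero, the coefficient exceeds both d and d − k.

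**5. Is k = 0 plausible here?** The Protocol's Intervention Summary has intervention schools checking wear daily (later twice daily), prompting prescribed children to wear their glasses and working with families. None of that is confined to pupils with two pairs and more than 80% attendance. Protocol Table 4 scores one pair as an incomplete set, above no glasses. A pupil whom the programme moves from no glasses to one pair stays at 0 in the compliance variable but may read better.

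**6. The null rule.** By step 2, a coefficient near zero says that the arms did not differ. It does not say why. Take k = 0 and p = 40%, so the exclusion restriction holds. The arm difference is 0.40 × 0.20 = 0.08 instead of 0.20 at full uptake, so non-compliance has cost 0.12. Yet 0.08 lies below the minimum detectable effect of 0.194 in SAP Table 2, so a non-significant result is likely. The rule also requires the effect to be non-meaningful, a term the SAP does not define.

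**The case against.** The strongest reply is that this is one loose sentence and one adjective in a supplementary analysis. The equations are ordinary 2SLS, the ITT analysis is primary and reported anyway, and the wording alters no estimate. All of that stands. Protocol Table 4 also already plans the percentage of treatment-school children with two pairs, though not the combined full-fidelity rate or a control-arm rate.

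Four stronger readings are tempting, and the documents do not support them.

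- A reader might infer that the SAP sets full compliers against minimal compliers alone. The sentence includes control pupils in the comparator, and that pooled group is the 0 category of the observed variable.
- A reader might infer that the trial cannot estimate an effect of full fidelity. Under the usual instrumental-variable assumptions it can, among compliers, and step 3 shows it doing so.
- A reader might infer that the report will label the result as full versus minimal compliance. No text specifies that label. The section says its purpose is to assess treatment effects when there is non-compliance, and it calls the result a CACE.
- A reader might size the error by comparing the described contrast with the coefficient. Assume 0.10 SD in every intervention pupil, equal arms, no selection and no control compliers. At p = 30%, 50% and 70% the described contrast is 0.059, 0.067 and 0.077, and the coefficient is 0.333, 0.200 and 0.143: ratios of 5.7, 3.0 and 1.9. These arise wholly because non-compliers are assumed to benefit. If only full compliers benefit, both quantities equal the complier effect and the ratio is 1.0.

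The reply does not rescue the closing paragraph. Its two interpretive statements are written in advance as conclusions, and neither follows from the equations.

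**Conclusion.** The point holds as a fault of interpretation. The SAP gives the predicted variable a meaning that only the observed variable has, omits the exclusion restriction, and commits to two readings that the coefficient cannot bear. The ITT result and the 2SLS estimate are unaffected.

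The wording error has no numerical size of its own. What can be sized is the consequence of the unstated assumption failing: with d = 0.20 and a partial effect of 0.10 to 0.20, the coefficient lies between 0.225 and 0.50 for full-fidelity rates of 80% down to 40%. Those rates and effects are assumptions, as is zero full fidelity in control. That partial delivery helps is likely from the programme's description but is not shown in the documents. The change is worth making because the error would reach the conclusions and is cheap to remove.

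**What to change.** 1. Replace the SAP sentence on what predicted compliance measures with:

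> The second-stage coefficient is the adjusted arm difference divided by the adjusted arm difference in full-fidelity rate. It estimates the effect of allocation among pupils who reach full fidelity only because their school was allocated to Glasses in Classes, assuming allocation has no effect on pupils whose full-fidelity status it does not change and makes no pupil less likely to reach full fidelity. It is not a comparison of fully with minimally compliant pupils. If partial delivery also helps, it overstates the effect of full fidelity.

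2. In the section's closing paragraph, delete the claim to "provide an unbiased estimate of the impact of compliance and non-compliance on the outcome", and delete the sentence that reads a null coefficient as showing that non-compliance had no impact.

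3. Report the full-fidelity rate by arm and the ITT estimate beside the CACE. The first stage already needs a compliance value for every control pupil, while Protocol Table 4 covers treatment schools only, so say whether the control value is observed or set to zero.

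The cost is a few sentences in the SAP and a few figures in one results table. The models do not change, and no data are needed beyond what the CACE analysis already requires.
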